#### Randomized, Double-Blind, Placebo-Controlled Part:

Screening: up to 8 weeks.

Treatment period: Subjects will remain on the same treatment assignment for up to 7 years.

**End-of-Study**: All 2000 subjects planned to be randomized into this study will receive Aramchol or matching placebo until EoS which will occur at the time when a total of 380 subjects will experience at least 1 pre-specified clinical event or at 5 years from last subject's randomization, whichever comes first.

Both study parts (Open Label Part and Randomized, Double Blind, Placebo Controlled Part):

**Study Visits:** All subjects will attend the following visits: Screening, Baseline, weeks 4, 8, 12, and every 12 weeks thereafter.

[figure not shown]
Visit scheduling for subjects who switch from the Randomized, Double-Blind, Placebo-Controlled Part to the Open-Label Part is dependent on prior exposure to Aramchol. Subjects that received active treatment will continue based on scheduled visits. Subjects that received placebo will start the scheduled visits from a Baseline visit

At the visit when the switch is performed, subjects will sign a new ICF and complete activities as applicable (e.g. laboratory, imaging, stool samples).

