## 10.1.2 Recording and Reporting Adverse Events

AEs fall into the categories of "nonserious" and "serious". All AEs must be recorded on source documents and eCRF from the time the subject has signed the informed consent until the EoS or early termination (ESD) visit, regardless of apparent causality from use of the study drug.

At each visit, subjects should voluntarily report any AEs in response to general nonleading questions (e.g., "How have you been feeling since your last visit?"). For each AE reported by subjects, clinical site personnel should obtain all required information to complete the eCRF.

The AE term, date of onset, severity, seriousness, action taken, Investigator opinion of relationship to the study drug, outcome and date of resolution will be recorded in source documents and eCRF following the Investigator's assessment. If an ongoing AE worsens or improves in its severity, the maximum severity that occurred over the duration of the event should be recorded in eCRF.

AE verbatim terms provided by the Investigator will be coded using the current Medical Dictionary for Regulatory Activities (MeDRA) Version.

AEs classified as serious must be recorded on the appropriate SAE form and reported using the expeditious handling of SAE procedures to comply with regulatory requirements (see Section 10.1.5.3).

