## 11.2 Randomized, Double-Blind, Placebo-Controlled Part:

A total of 2000 subjects will be randomized into this study in a 2:1 ratio to treatment with Aramchol or with placebo, respectively.

An eligible subject will randomly be allocated to treatment with Aramchol or matching placebo based on a randomization scheme employing a 2:1 assignment ratio, respectively, using permuted blocks stratified by country/geographical region (CGR) and by baseline Fibrosis stage (F2 or F3).

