#### 11.3.1 Adverse Events

An AE is any untoward medical occurrence in a subject administered a pharmaceutical product, regardless of whether it has a causal relationship with this treatment. In this study, any AE occurring after the subject has signed the ICF should be recorded and reported as an AE.

The MedDRA dictionary will be used to standardize the terms used by the Investigator to describe the AEs.

The following will be incorporated into the analysis of adverse events:

- As analysis of AEs can incorporate only coded AEs, it is mandatory that at the time of database lock all AEs will be coded.
- Adverse events analyses will include only the Treatment Emergent Adverse Events
  (TEAEs), namely, those events which started on the day of randomization or afterwards.
  AEs lacking start day will be considered as TEAE.
- Analyses of TEAEs will include the display of cumulative incidence proportions (no. of subjects reporting at least one TEAE per category), exposure adjusted incidence rates of the number of TEAEs, and estimated differences and confidence intervals for all pairwise treatment arm comparisons.

The following analyses which are pre-planned for adverse events will include:

- Most frequent TEAEs (>5% of subjects in at least one study arm) by Preferred Term (PT).
- TEAEs broken down by System Organ Class (SOC) and by SOC and PT according to MedDRA dictionary.
- Serious TEAEs by MedDRA SOC and PT, data listing as well as summary table of SAEs broken down by study trimesters (90 days each).
- TEAEs broken down by severity.
- TEAEs broken down by relationship to study drug.
- TEAEs broken down by action taken.
- TEAEs broken down by event outcome.
- TEAEs will be provided broken down by study group and subgroups.
- Adverse Events dictionary used to code Investigator's verbatim terms will also be provided.
- Individual subject listings of TEAEs and non-TEAEs.

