## 11.4 Tolerability Assessments

Tolerability assessment will be based on the number and percent (%) of subjects who early discontinued treatment (ETD) and early discontinued study (ESD) by withdrawal reason will be presented. Time to withdrawal will also be presented by Kaplan-Meier curves.

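### The TEAE cumulative incidence in Section 11.3.1 is a crude subject proportion over unequal follow-up, so its between-arm difference can mislead if study discontinuation differs by arm

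*Combined protocol and SAP*

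**What the plan says.** All references are to the combined protocol and SAP.

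- **Measures.** Section 11.3.1 plans two measures in one sentence. The first is "cumulative incidence proportions (no. of subjects reporting at least one TEAE per category"). The second follows at once: "exposure adjusted incidence rates of the number of TEAEs, and estimated differences and confidence intervals for all pairwise treatment arm comparisons". The differences and intervals are named once, after both measures. Sections 11.3.2 to 11.3.4 repeat the pair for laboratory, vital-sign and ECG events.
- **Observation window.** TEAEs are "those events which started on the day of randomization or afterwards" (11.3.1), with no end tied to the last dose. Section 10.1.2 has adverse events recorded "from the time the subject has signed the informed consent until the EoS or early termination (ESD) visit".
- **Length of follow-up.** Section 8.1 states: "Subjects will remain on the same treatment assignment for up to 7 years". The study ends at 380 subjects with a clinical event or "at 5 years from last subject's randomization, whichever comes first".
- **Size.** Section 11.2 states: "A total of 2000 subjects will be randomized into this study in a 2:1 ratio", which is about 1333 Aramchol and 667 placebo.
- **Two kinds of discontinuation.** Under Section 8.1, a subject who stops drug (ETD) stays on the visit schedule. Only ESD ends observation.
- **Time-to-event displays.** Section 11.4 states: "Time to withdrawal will also be presented by Kaplan-Meier curves". Section 11.3.1 splits SAEs by 90-day periods. The text available plans no time-to-first-event estimate for TEAEs.

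**The concern.** A cumulative incidence is the probability of a first event by a stated time. A count of subjects with at least one event, divided by the number in the arm, estimates that probability only if everyone is observed to that time. Here a subject who leaves without an event stays in the denominator as event-free, although nothing is known about the later years.

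The loss is harmless to a null comparison if both arms lose observation time equally. If one arm leaves the study faster, its proportion is lowered more and the difference moves in its favour. The confidence interval does not reflect this, because it treats the proportions as fully observed.

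At stake is how the long-term safety comparison is read, in particular whether a real excess on Aramchol could look smaller than it is.

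**Working it through.** The plan states no TEAE rate, no exit rate by arm and no safety precision, so there is no figure of its own to reproduce. The numbers below are illustrations.

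**Inputs**
- Arm sizes 1333 and 667, from 2000 subjects at 2:1 (Section 11.2).
- Placebo exit hazard, assumed. Section 3.2 reports that almost 90% of the active-arm subjects in the Phase 2b study completed 65 weeks. As a constant hazard, D0 = -ln(0.90)/(65/52) = 0.084 per year.
- Ratio of Aramchol to placebo exit, assumed: 1, 1.25, 1.5 or 2.
- Event hazard L, assumed: 0.05 or 0.10 per year. Follow-up T, assumed: 5, 5.5 or 7 years.

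**Formulas** (constant hazards; exit independent of the event)
- True risk = 1 - exp(-L·T).
- Expected crude proportion = L/(L+D) × [1 - exp(-(L+D)·T)].
- SE = √[pA(1-pA)/1333 + pP(1-pP)/667] and B = difference/SE.
- Coverage of the 95% interval when the true difference is zero = Φ(1.96-B) - Φ(-1.96-B).

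**No true difference, L = 0.05, T = 5, placebo exit 0.084.** The true risk is 22.1% in both arms. The placebo crude proportion is 0.05/0.1343 × [1 - exp(-0.671)] = 18.2%.

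| Aramchol exit | Crude, Aramchol | Difference (points) | Coverage |
|---|---|---|---|
| ×1 | 18.2% | 0.0 | 95% |
| ×1.25 | 17.4% | -0.8 | 93% |
| ×1.5 | 16.6% | -1.6 | 86% |
| ×2 | 15.2% | -3.0 | 61% |

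Longer follow-up or commoner events enlarge the effect. At ×1.5 the difference is -2.6 points over 7 years. With L = 0.10 it is -2.7 points over 5 years and -4.2 over 7.

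**No true difference, twofold exit, T = 5.5, other assumed rates**
- L = 0.10, exit 6% vs 3% per year: 0.10/0.16 × [1 - exp(-0.88)] = 36.6% against 0.10/0.13 × [1 - exp(-0.715)] = 39.3%. The difference is -2.7 points and coverage is 78%.
- L = 0.10, exit 10% vs 5%: -4.1 points, coverage 56%.
- L = 0.05, exit 6% vs 3%: -1.6 points, coverage 87%.

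**A true excess: hazard ratio 1.3, L = 0.05 on placebo, T = 5, placebo exit 0.084.** The true risks are 27.7% and 22.1%, a difference of 5.6 points. The crude difference is 4.7 points with equal exit (22.9% vs 18.2%), 2.7 at ×1.5 and 1.0 at ×2.

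**The exposure-adjusted rate.** With a constant hazard it is unbiased whatever the exit pattern. Now suppose events come early: 0.20 per year in year 1 and 0.05 after that, the same in both arms, over 5 years. Person-years per subject at exit D0 are 0.959 in year 1 and 3.121 later, so the rate is (0.20×0.959 + 0.05×3.121)/4.080 = 0.085. At ×1.5 it is (0.20×0.939 + 0.05×2.767)/3.706 = 0.088, and at ×2 it is 0.091. The rate rises in the arm that leaves earlier while the crude proportion falls, so the two planned measures can point in opposite directions.

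**The case against.** A reader might infer that the planned differences and intervals are biased as they stand, or that a poorly tolerated drug will look safer. The documents do not support either reading.

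- **Differential exit is not shown.** No section reports or assumes that ESD differs by arm, and randomization balances staggered entry. With equal exit the null difference is zero and coverage is nominal. At 1.25-fold exit, coverage in the 5-year example is still 93%.
- **Stopping drug is not leaving the study.** ETD subjects stay under observation. Section 8.2.8 asks sites to retain them and offers reduced visits, telephone contact, annual follow-up and record access. A subject who has a TEAE before leaving is counted, including one who leaves because of it. The model above, with exit independent of the event, is therefore a poor picture of intolerance.
- **A person-time measure is already planned**, in the same sentence, and is unbiased under a constant hazard. The crude proportion does not stand alone.
- **Withdrawal will be visible.** Section 11.4 tabulates ETD and ESD by reason and plots time to withdrawal, which helps reveal the condition that the bias needs.
- **Other text may exist.** Section 8.4.3 mentions a more detailed SAP. That document and the definitions of the safety sets are not in the text available.

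These points make the bias conditional and limit its likely size. They do not remove the gap. Section 8.2.8 itself expects some ETD subjects to withdraw later, and it requires ESD after emergency unblinding or the start of an approved NASH drug; either could occur unequally. The rate counts events, so repeat events in one subject add up, and it gives no risk per subject. Exposure is not defined as time on drug or time in study. Attenuation of a true difference does not need unequal exit.

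**Conclusion.** The point holds in conditional form. The measure that Section 11.3.1 calls cumulative incidence is a crude proportion over variable follow-up, and its between-arm difference can favour the arm that leaves the study earlier.

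With no true difference, the illustrated bias is -0.8 points at 1.25-fold exit, -1.6 at 1.5-fold (both 5 years, 5%/year event hazard, 8.4%/year placebo exit) and -1.6 to -4.1 at twofold (5.5 years, other assumed rates). Equal exit gives no null bias but reduces a true 5.6-point excess to 4.7 at a hazard ratio of 1.3. The exposure-adjusted rate mitigates this only partly.

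All sizes rest on assumed constant hazards, assumed exit ratios and exit independent of the event. Only the arm sizes and the Phase 2b completion figure come from the documents. This is a cheap improvement to the safety analysis; it does not show that the planned comparison will be wrong.

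**What to change.** In Section 11.3.1, for serious TEAEs, TEAEs of special interest and the most frequent TEAEs:

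- Add the Aalen-Johansen cumulative incidence of time to first event, with death as a competing event and censoring at ESD or data cut-off.
- Report the between-arm difference with a 95% CI at week 72 and at one late time point with adequate numbers at risk, for example year 5 if it is reached.
- Base the between-arm risk comparison for these categories on this estimate. Keep the crude n (%) and the exposure-adjusted rates as descriptive or supportive.
- Name the special-interest categories in advance, and state whether exposure means time on drug or time in study.

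The laboratory, vital-sign and ECG tables may stay as planned. Abnormalities there are found at visits, so their onset times are only known to an interval, and the extra work would gain little.

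The cost is SAP wording and some programming; onset dates are already collected, and study exit is already documented. The estimates refer to fixed time points, the late one may be thin if 380 events end the study early, and censoring at ESD assumes that exit is independent of adverse-event risk within arm. That assumption should be stated beside the results.

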#### 11.3.2 Laboratory Data

Laboratory testing will be performed by a central laboratory facility and/or affiliated laboratories which work under the central laboratory regulations using the same reference normal ranges.

Analyses of safety central laboratory data will be performed in the following manner:

- Analyses events as defined below will include the display of cumulative incidence proportions (no. of subjects reporting at least one event per category), exposure adjusted incidence rates of the number of events, and estimated differences and confidence intervals for all pairwise treatment arm comparisons:
  - ✓ Post-randomization Potential Clinical Significance (PCS) lab values will be provided.
  - ✓ Abnormal values at any time after randomization day, calculated for subjects with normal values at baseline will be provided. Analysis will include, per tested parameter, those subjects with normal baseline and at least one post-randomization day measurements.
  - ✓ The distribution of maximal values of central laboratory AST, ALT and total bilirubin at any time after randomization day in term of the upper normal range multiples will be provided for subjects with normal AST, ALT and total bilirubin at baseline.

- Quantitative laboratory measurements will be categorized with reference to the normal ranges as Low, Normal or High. Shift analysis of the categorical change from baseline to each scheduled visit and to the last observed value will be provided.
- Box-Plots of measurements done, figures of mean values ±SEs of changes from baseline as well as descriptive statistics for all laboratory quantitative parameters and changes from baseline will be provided by scheduled visits and treatment groups.

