#### Close Observation

- Repeating liver enzyme and serum bilirubin tests two or three times weekly. Frequency
  of retesting can decrease to once a week or less if abnormalities stabilize or study drug
  has been discontinued and the subject is asymptomatic.
- Obtaining a more detailed history of symptoms and prior or concurrent diseases.
- Obtaining a history of concomitant drug use (including nonprescription medications and herbal and dietary supplement preparations), alcohol use, recreational drug use, and special diets.
- Ruling out acute viral hepatitis types A, B, C, D, and E; autoimmune or alcoholic hepatitis; hypoxic/ischemic hepatopathy; and biliary tract disease.
- Obtaining a history of exposure to environmental chemical agents.
- Obtaining additional tests to evaluate liver function, as appropriate (e.g., INR, direct bilirubin). In case of discontinuation, study drug can be restarted only if another etiology is identified and liver enzymes have returned to normal levels.

If after re-challenge, a subject experiences DILI (i.e., recurrent elevations of total bilirubin, ALT, or AST), irrespective of the magnitude of liver enzymes elevation, the study drug should be discontinued permanently.

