#### 11.3.3 Vital Signs

Vital signs will be analyzed in the following manner:

- Cumulative incidence proportions (no. of subjects reporting at least one event), exposure
  adjusted incidence rates of the number of events, and estimated differences and
  confidence intervals for all pairwise treatment arm comparisons of post-randomization
  Potential Clinical Significance (PCS) vital signs values will be provided.
- Box-Plots of measurements done, figures of mean values ±SEs as well as descriptive statistics for all parameters and changes from baseline will be provided by scheduled visits and treatment groups.

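### The exposure-adjusted rates for abnormal laboratory, vital-sign and ECG values count readings rather than subjects, so they partly measure testing frequency

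*Combined protocol and SAP*

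**What the plan says.** Section 11.3.2 plans two measures side by side. One is subject-based: "cumulative incidence proportions (no. of subjects reporting at least one event per category". The other is event-based: "exposure adjusted incidence rates of the number of events, and estimated differences and confidence intervals for all pairwise treatment arm comparisons". The events include PCS values ("Post-randomization Potential Clinical Significance (PCS) lab values will be provided") and new abnormalities ("Abnormal values at any time after randomization day, calculated for subjects with normal values at baseline will be provided"). Sections 11.3.3 and 11.3.4 use the same event-based numerator for PCS vital signs and ECG values ("adjusted incidence rates of the number of events"). Section 11.3.1 plans "exposure adjusted incidence rates of the number of TEAEs" for TEAEs.

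Readings are frequent. Section 8.1 sets visits at weeks 4, 8 and 12 and then every 12 weeks, for up to 7 years. Biochemistry and ECG are done at every visit, and vital signs also at unscheduled visits (8.2.5, 9.9.4, 9.9.6). Under section 7.5.2.1.1 a transaminase rise triggers a confirmatory test within 48 to 72 hours, and close observation then means "Repeating liver enzyme and serum bilirubin tests two or three times weekly".

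The available text does not say whether consecutive abnormal readings form one episode or whether unscheduled retests count. It gives no variance method or CI level for the safety rates.

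**The concern.** Section 11.3.2 separates subjects from events within one sentence, so the natural reading is that each qualifying value is an event. A subject whose value stays abnormal then adds one event per visit, and a subject under liver observation may add several within weeks. The numerator mixes how many subjects were affected, how long the abnormality lasted and how often it was tested.

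Two things follow. The rate is hard to interpret as a risk. Readings within a subject are also correlated, so an interval that treats them as independent understates the uncertainty, and a few subjects could create an apparent difference between arms. The proportions beside it are not affected, but they do not adjust for follow-up, which varies with entry date and early discontinuation.

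**Working it through.** Section 11.3 states no rate, variance formula or CI width, so there is no figure to reproduce. The check below is conditional on two things: every abnormal reading counts, and the CI is a 95% Poisson interval.

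**Inputs from the documents.** 2000 subjects randomized 2:1, about 1333 and 667 (11.2). Post-baseline visits counted from 8.1: 8 by week 72, 23 by week 260, 32 by week 364.

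**Assumed inputs.** A share p of 5%, 10% or 20% of subjects ever abnormal, the same in both arms. Onset is equally likely at any visit. The number of abnormal readings D per affected subject is either geometric with mean 3 visits (transient) or runs from onset to the end (persistent).

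**Formula.** A subject contributes D readings with probability p, otherwise 0.
- Mean = p·E[D]; variance = p·E[D²] − p²·E[D]².
- Variance/mean: φ = E[D²]/E[D] − p·E[D].
- The correct CI is √φ times the Poisson width; Poisson coverage = 2Φ(1.96/√φ) − 1.

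**Example: 5 years, p = 10%, persistent.** D is uniform on 1 to 23, so E[D] = 12 and E[D²] = 24 × 47/6 = 188.
- φ = 188/12 − 0.10 × 12 = 15.67 − 1.20 = 14.47, and √φ = 3.80.
- Coverage = 2Φ(1.96/3.80) − 1 = 39%.
- Rate counting readings: 0.10 × 12/5 = 24.0 per 100 person-years. Counting each subject once over total follow-up: 0.10/5 = 2.0. With person-time stopped at first event (on average half-way): 0.10/(0.90 × 5 + 0.10 × 2.5) = 2.1.

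**Simulation (3000 trials per setting, full follow-up, p = 5–20% unless stated).**

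| Follow-up | Pattern | Poisson coverage | Correct/Poisson width |
|---|---|---|---|
| 72 weeks | transient | 73–76% | 1.7–1.8 |
| 72 weeks | persistent | 60–63% | 2.2–2.3 |
| 5 years | transient | 66–68% | 2.0–2.1 |
| 5 years | persistent | 39–42% | 3.6–3.9 |
| 5 years | transient, p = 10%, plus 6 retests | 50% | 2.9 |
| 5 years | persistent, p = 5%, plus 6 retests | 34% | 4.4 |

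A subject-level (robust) variance gives 94–96% coverage in every row.

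**Shorter durations, follow-up spread over 2–5 years, p = 5–10%.** The Poisson CI excludes zero in roughly 21% of trials when abnormalities average 2 visits and 56% when they persist. For a geometric mean of 2 visits, E[D²] = 6, so φ = 6/2 − 0.05 × 2 = 2.9 and 2(1 − Φ(1.96/1.70)) = 25%; truncation at the end of follow-up lowers this to the low twenties. If every abnormality lasted exactly 2 visits, φ = 4/2 − 0.10 = 1.9 and the figure is about 16%. With one reading per affected subject, φ = 1 − p and there is no inflation. The effect therefore comes entirely from repeats, which is why a first-event rate removes it.

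**TEAEs.** With negative-binomial counts, φ = 1 + k × rate × T, for k = 0.5–2 and T from 72 weeks to 5 years.

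| TEAE rate per person-year | Correct/Poisson width | Poisson coverage |
|---|---|---|
| 0.01 (rare term) | 1.00–1.05 | 94–95% |
| 0.1 | 1.03–1.41 | 83–94% |
| 1 (pooled TEAEs) | 1.3–3.3 | 45–87% |

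For example, at 1 per person-year with k = 1 and T = 3, φ = 4 and coverage = 2Φ(1.96/2) − 1 = 67%.

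**The case against.** The strongest reply is that nothing here is a demonstrated error. A reader might infer that the planned CIs are far too narrow. The documents do not support that, because no CI method is given and a robust variance would restore about 95% coverage. Section 8.4.3 mentions a more detailed SAP, and part of the statistical section is not in the available text, so an episode rule or variance method may exist elsewhere. This stands, and it makes the size conditional. It does not change the numerator, which is stated.

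A reader might also infer that these rates are the main safety comparison. The plan does not say so. Subject-level proportions come first in each section, and the CIs in the same sentence can be read as covering them. Section 11.3.2 adds maximal AST, ALT and bilirubin (one value per subject) and shift tables, and suspected liver injury is adjudicated (section 10). None of these is inflated by repeats.

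Nor do persistent adverse events inflate the TEAE count. Section 10.1.2 records an ongoing event that changes severity once, at its maximum, and an event rate is a legitimate measure for adverse events. Only clustering of true recurrences remains.

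The number of extra readings per liver episode cannot be derived. Section 7.5.2.1.1 lets testing fall to weekly or less, section 7.5.2.1 gives a different retest frequency, and neither says that retests enter the safety counts.

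Finally, repeats raise the rate in both arms, so bias between arms needs retesting or persistence to differ. The documents show a route but no direction: section 3.2 reports lower ALT and AST on active treatment, and for abnormal baselines the retest trigger is relative to baseline (7.5.2.1.1), which can be reset downward (7.5.2.1).

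**Conclusion.** The point holds for PCS and abnormal values in 11.3.2 to 11.3.4. Their only exposure-adjusted comparison between arms counts events as written, so it depends on visit frequency, persistence and possibly triggered retests.

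The loss of precision is conditional on an independence (Poisson) interval. On that assumption, with equal arms, 5–10% of subjects ever abnormal, an average duration of 2 visits or more and 2–5 years of follow-up, zero is excluded in roughly 21–56% of trials instead of 5%. Prevalence, duration and dispersion are assumptions, not figures from the plan. For TEAEs the rate itself is sound; the variance matters for frequent or pooled terms and is negligible for rare ones.

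**What to change.** - **11.3.2 to 11.3.4:** for PCS and abnormal values, define the exposure-adjusted rate as subjects with a first event divided by person-time to that event or end of observation. Base the between-arm differences and CIs on it. Show counts of readings as descriptive totals without CIs.
- **11.3.1:** keep the TEAE event rate, but compute any between-arm CI with a subject-clustered (robust) or negative-binomial variance.

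The cost is a few lines of SAP text and minor programming. Section 8.4.3 already foresees a SAP amendment before the blind is broken for the histology analysis, which is a suitable place. The downside is that recurrence of abnormal values no longer enters the interval; the descriptive totals still show it.
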